11 DATA HANDLING AND RECORDKEEPING

11.1 Data Management Responsibilities

Study case report forms will be developed by the SDMC. Quality control reports and queries routinely will be generated and distributed to the study sites for verification and resolution.

11.2 Source Documents and Access to Source Data/Documents

The investigator will maintain, and store securely, complete, accurate and current study records throughout the study. In accordance with U.S. regulations, the investigator will retain all study records indefinitely. Study records will not be destroyed prior to receiving approval for record destruction from DAIDS and Starpharma. Applicable records include source documents, site registration documents and reports, correspondence, informed consent forms, and notations of all contacts with the participant.

11.3 Quality Control and Quality Assurance

[name], who completed a training program in clinical and public health microbiology certified by the American Board of Medical Board of Microbiology, directs the Site Support and Diagnostic Training Core in the MTN Network Laboratory at Magee-Womens Research Institute. This laboratory is Clinical Laboratory Improvement

Amendments (CLIA)-inspected and maintains its own CLIA license. Thus, all testing done in this research laboratory is performed with the same level of quality control as required in a licensed clinical laboratory.

[name] directs the Virology Core in the MTN Network Laboratory at the University of Pittsburgh School Of Medicine. This laboratory is CLIA-certified and has consistently met proficiency standards for HIV-1 RNA testing established by the DAIDS-sponsored Virology Quality Assurance program. All HIV-1 endpoint confirmations will be done in this laboratory.

See Section 12 for site monitoring plan.

11.4 Study Coordination

Starpharma Pty Ltd holds the IND application for this study (#62,482). Assignment of all sponsor responsibilities for this study will be specified in a Clinical Trials Agreement executed by DAIDS, NICHD, and Starpharma Pty Ltd. Study site staff will be provided with the DAIDS SOPs for Source Documentation and Essential Documents, the Manual for Expedited Reporting of Adverse Events to DAIDS, and the DAIDS AE Grading Table. Training and written instructions outlining management and reporting, study gel dispensing, product accountability, and other study operations will be provided by Family Health International, the Statistical Center for HIV/AIDS Research & Prevention (SCHARP), and the MTN Network Laboratory. The final study report will be consistent with both DAIDS and ICH E3 guidelines.

12 CLINICAL SITE MONITORING

Study monitoring will be carried out by Westat (Rockville, MD). On-site study monitoring will be performed in accordance with DAIDS policies. Site monitoring visits will be conducted to assess compliance with Health and Human Services (HHS) Regulations 45 CFR Part 46 and 21 CFR Parts 50, 56, and 312. Study monitors will visit the site to:

- Verify compliance with human subjects and other research regulations and guidelines, including confidentiality procedures, informed consent process, and regulatory documentation
- Assess adherence to the study protocol, study-specific procedures manual, and local counseling practices, including compliance related to study product management and pharmacy-related procedures
- Confirm the quality and accuracy of information collected at the study site and entered into the study database, including the validation of data reported on case report and DataFax forms

- Assess the resolution of any past or ongoing issues identified at previous monitoring visits

A minimum of three monitoring visits per site will occur for this study, including a visit shortly after study initiation, one at the perceived midpoint for enrollment, and a third for study closeout.

Site investigators will allow study monitors to inspect study facilities and documentation (e.g., informed consent forms, clinic and laboratory records, other source documents, case report forms), as well as observe the performance of study procedures. Investigators also will allow inspection of all study-related documentation by authorized representatives of the MTN CORE, MTN NL, Family Health International, Statistical Center for HIV/AIDS Research & Prevention, NIAID, NICHD, Starpharma Pty Ltd, FDA, and US regulatory authorities. A site visit log will be maintained at the study site to document all visits.

13 HUMAN SUBJECTS PROTECTIONS

The investigators will make efforts to minimize risks of this new product to human participants. Volunteers will take part in a thorough informed consent process throughout their participation in the study. Before beginning the study, the investigators will have obtained IRB approval and the protocol will have been submitted to the FDA. The investigators will permit audits by the NIH, Starpharma Pty Ltd or the FDA or any of their appointed agents.

13.1 Institutional Review Boards

Each participating institution is responsible for assuring that this protocol and the associated informed consent documents and study-related documents are reviewed by an Ethics Committee (EC) or Institutional Review Board (IRB) prior to implementation of the protocol. Any amendments to the protocol, informed consents, or other study-related documents must be approved by the EC/IRB, NICHD, and DAIDS prior to implementation.

13.2 Protocol Registration

Each participating institution will complete protocol registration with the NICHD via Westat. After study sites have received final approval from their local IRB, they must submit protocol registration materials to the Data and Operations Center (DOC) at Westat in accordance with ATN requirements. When the DOC has received all required registration materials, the DOC will approve the site's protocol registration and notify the site that it may begin protocol enrollment. Protocol registration must occur before the site can enroll any participants into the study.

The study will be conducted in full compliance with the protocol. The protocol will not be amended without prior written approval by the Protocol Chair, NIAID Medical Officer, and NICHD Medical Officer. All protocol amendments must be submitted to and approved by the relevant IRB(s), and where necessary by Starpharma to the FDA, prior to implementing the amendment.

Following ethical review and approval, study sites will submit required administrative documentation to the ATN DOC, Westat. NICHD has delegated responsibility for review and approval of protocol-specific regulatory documentation to Westat. Included in this step will be MTN CORE review of each site-specific study informed consent form.

13.3 Risk/Benefit Statement

Risks

Before testing in humans VivaGel[®] and the active ingredient were tested in animals. VivaGel[®] was well tolerated in a number of animal studies using rats, mice, guinea pigs, dogs, rabbits and monkeys. At one laboratory, some rabbits died when they received VivaGel[®] in the vagina at various doses similar to those that will be used in this study. However, this effect was not seen in other studies when VivaGel[®] was applied to the vaginas of female rats, dogs, monkeys, and in other studies in rabbits at one other laboratory, in which no rabbits died. Further investigation indicated that the deaths of the rabbits were likely to be related to the procedure used at that laboratory to administer the VivaGel[®] to the vagina. Rabbits have a place in the vaginal wall where blood vessels are concentrated. It was concluded that damage was caused to that area of the vaginal wall by the dosing procedure, which in turn caused bleeding. Humans, monkeys and rats do not have this concentration of blood vessels in the vagina. It is considered that the effects seen in that rabbit study do not represent a risk to the participants in this or any other clinical trial of VivaGel[®]. However, the researchers could not determine the exact cause of death in these rabbits.

It is not expected that this trial will expose participants to unreasonable risk. The intervention used in this study is unlikely to cause uncomfortable side effects. An unpublished clinical study suggests a low incidence of side effects, both in the VivaGel[®] and placebo gel groups.

In the first clinical study of VivaGel[®] (Starpharma Protocol Number SPL7013-001), volunteers reported the following adverse events that were deemed at least possibly related to study product: vaginal pruritus, vaginal discharge (including product leakage), abdominal discomfort or pain, and dysuria. A rare but potentially life-threatening risk of exposure to either study agent would be anaphylaxis (has not yet been reported for either VivaGel[®] or placebo gel). Use of a vaginal applicator may cause discomfort, and rarely, vaginal or cervical injury. Colposcopy may also cause mild discomfort secondary to speculum placement in the vagina for the 10-15 minute examination. Collection of cervical cells by Cytobrush[®] may cause discomfort or spotting during specimen

collection. Phlebotomy may lead to discomfort, feelings of dizziness or faintness, and/or bruising, swelling and/or infection.

Male sexual partners will be protected from potential risks of study drug exposure by the use of condoms throughout the study.

Disclosure of STI status may cause sadness or depression in volunteers. Disclosure of HIV-positive status has been associated with depression, suicidal ideation, and denial, as well as social isolation. Participation in clinical research includes the risks of loss of confidentiality and discomfort with personal nature of questions.

Benefits

Participation in this Phase 1 trial likely will have no direct benefit to volunteers other than access to screening for STIs and appropriate referral if STIs are diagnosed. Some volunteers may have the opportunity to access expedient treatment and decreased morbidity due to early diagnosis and treatment of abnormalities in serology, blood count, coagulation, liver or kidney function tests. Pap smear and colposcopy may offer the opportunity for early detection of a cervical and/or vaginal abnormality with expedient referral if an abnormality is detected. Lastly, the participant may appreciate the opportunity to contribute to the body of knowledge in the field of microbicide research. However, there is no guarantee that volunteers will receive any of these benefits.

13.4 Informed Consent Process

Written informed consent will be obtained from all potential study participants prior to the initiation of any study-related procedures. In obtaining and documenting informed consent, the investigators will comply with applicable local and domestic regulatory requirements and will adhere to GCP and to the ethical principles that have their origin in the Declaration of Helsinki.

Prior to the beginning of the trial, site investigators will have the IRB/EC's written approval/favorable opinion of the protocol, informed consent forms, and any other study-related information to be provided to participants. This study does not plan to enroll children under 18 or illiterate individuals. All study related materials including the informed consent forms will be available in English and Spanish as required by each study site.

The informed consent process will give individuals all of the relevant information they need in order to decide whether to participate, or to continue participation, in this study. Potential research participants will be permitted to ask questions and to exchange information freely with the study investigators. Only listed study investigators may obtain informed consent from potential study participants. The investigators will keep research participants fully informed of any new information that could affect their willingness to continue study participation.

13.5 Participant Confidentiality

Members of the study staff sites are all trained in patient confidentiality for their participation in the ATN. The only sites at which this study will be performed are both ATN Trials Units (ATU). The log of study participant names and other protected health information will be kept in a double-locked area. All computer information about study volunteers will be kept on a computer with log-on passwords. Laboratory specimens are labeled with study numbers and date, and are delivered or shipped by study staff. The study sites' data management and clinical staff are the only personnel with access to the protected health information of study volunteers. Each member of the staff has log-on identification and password, logs off before leaving a computer screen unattended, and closes their office door when out of the office. All research records will be kept indefinitely following closure of this study.

To further protect the privacy of the study participants, the ATN has obtained a Certificate of Confidentiality from the U.S. Department of Health and Human Services (DHHS). With this Certificate in place, the ATN researchers cannot be forced to turn over identifying information about a study participant in any Federal, State, or local criminal, administrative, legislative, or other proceedings. This Certificate does not prevent a study participant from volunteering to turn over their research information nor does it prevent researchers from providing research-related information to others when requested by the study participant.

13.6 Special Populations

This section outlines considerations made for the inclusion or exclusion of special populations in this study.

13.6.1 Pregnant Women

Pregnancy is an exclusion criterion because there are no current recommendations for the use of VivaGel[®] during pregnancy. A urine pregnancy test will be performed on all women at all clinic visits, and positive tests will be noted on the Eligibility Criteria form. During the informed consent process, women will be informed that VivaGel[®] is not known to prevent pregnancy and that the effect of VivaGel[®] on a developing human fetus is unknown. All potential participants will be required by the Eligibility Criteria for Screening and Enrollment to be currently using a reliable method of contraception, such as hormonal contraception (except vaginal ring), intrauterine device, or sterilization. Women who become pregnant during the study period following randomization and exposure to study product will discontinue product use but not be excluded from analysis.

13.6.2 Children

The NIH has mandated that children be included in research trials when appropriate. This study will enroll women aged 18 to 24 who are able to give informed consent. This study meets “Justifications for Exclusion” criteria for younger children as set forth by the NIH. Specifically, “insufficient data are available in adults to judge potential risk in children” and “children should not be the initial group to be involved in research studies.

13.7 Incentives

Pending IRB approval, participants will be compensated for their time and effort in this study, and/or be reimbursed for travel to study visits and time away from work. Site-specific reimbursement amounts will be specified in the study informed consent forms.

13.8 Communicable Disease Reporting

Study staff will comply with all applicable local requirements to report communicable diseases including HIV identified among study participants to local health authorities. Participants will be made aware of all reporting requirements during the study informed consent process.

13.9 Access to HIV-Related Care

This section outlines study participants’ access to HIV-related care, including HIV counseling and testing, as well as care for participants identified as HIV-infected.

13.9.1 HIV Counseling and Testing

HIV pretest and post-test counseling will be provided to all potential study participants who consent to undergo HIV screening to determine their eligibility for this study. Participants must receive their HIV test results to take part in this study. The investigators do not expect a screening population at high risk for HIV infection. However, trained clinical staff will refer participants who are confirmed to be HIV-infected per the HIV Antibody Testing Algorithm in Appendix III to a physician for follow-up testing and care. Participants who have positive or indeterminate results will have standard post-test counseling as well as limited follow-up confirmatory testing provided by the study. Referral for additional counseling related to testing or diagnosis will occur if needed or requested by the participant.

13.9.2 Care for Participants Identified as HIV-Infected

Study staff will provide participants with their HIV test results in the context of post-test counseling. According to site SOPs, study staff will refer participants found to be HIV-infected to available sources of medical and psychological care, social support, and local research studies for HIV-infected women.

13.10 Study Discontinuation

This study may be discontinued at any time by NIAID, NICHD, the MTN, Starpharma, the US FDA, other government or regulatory authorities, or site IRBs.

14 PUBLICATION POLICY

DAIDS and MTN policies and a Memorandum of Agreement (MOA) between MTN and ATN, and a Clinical Trial Agreement (CTA) between Starpharma, NICHD and NIAID, will govern publication of the results of this study. Any presentation, abstract, or manuscript will be submitted by the Investigator to the MTN Manuscript Review Committee, DAIDS, NICHD and Starpharma Pty Ltd, for review prior to submission.

APPENDICES

APPENDIX I: SCHEDULE OF STUDY VISITS AND EVALUATIONS

	Screen 1	Screen 2	Enroll	Phone Call	1-Week Clinic Visit	2-Week Clinic Visit	3-Week Clinic Visit	Inter./Safety Visit
Target Day	≤30 Days		Day 0	Day 2	Day 7	Day 14	Day 21	PRN
Window Period	≤36 Days		Day 0	Day 2-4	Day 6 – 8	Day 13 – 15	Day 20 – 24	
Study Communications								
Informed Consent	X		X					
Assign Participant ID	X							
Eligibility Assessment	X	X	▲					
Collect Demographics	X							
HIV Pre- & Post-Test Counseling	X							
Screening Results (as available)	X	X	X					
Treatment or Referral	▲	▲	▲		▲	▲	▲	▲
Record/Update Medical and Menstrual History	X	X	X		X	X	X	X
Baseline Behavioral Questionnaire			X					
Record/Update Con. Meds.			X		X	X	X	▲
Record Adverse Events					X	X	X	▲
Vaginal Product History			X					
Acceptability Assessment						X		
Adherence Assessment					X	X		
Male Condom Counseling	X	X	X		X	X		▲
Record/Update Contacts	X	X	X		X	X	X	X
Schedule Next Visit	X	▲	X		X	X	▲	▲
Obtain Random Assignment			X					
Phone Assessment				X				
Study Burden Questionnaire							X	
Reimbursement	X	X	X		X	X	X	
Laboratory								
Qual. Urine Pregnancy Test	X	X	▲		X	X	X	X
Urinalysis	X		▲		▲	▲	▲	▲
Urine Culture & Sensitivity	▲		▲		▲	▲	▲	▲
CBC, Liver Function Panel, Creatinine Level, Coag. Panel	X		X		X	X	▲	▲
RPR (Syphilis)	X		▲		▲	▲	▲	▲
Confirmatory Tests for Syphilis	▲		▲		▲	▲	▲	▲
HIV Antibody Screen	X							▲
HIV Confirmatory Testing	▲							▲
SPL7013 Level			X			X		
Plasma Archive			X			X		
Vaginal pH	X		X		X	X	X	▲
Quantitative Vaginal Cultures			X		X	X	X	▲
Vaginal Wet Prep Slide	X		X		X	X	X	▲
Gram-Stained Vaginal Smears	X		X		X	X	X	▲
Cervical Swabs for Cytokines and Innate Factors			X		X	X	X	▲
Urine SDA for Gonorrhea & Chlamydia	X		▲					
Genprobe Aptima					▲	▲	▲	▲
Pap Smear of Cervix	X							▲
Herpes Culture	▲				▲	▲	▲	▲
Clinical								
Colposcopy			X		▲	X	▲	▲
Vital Signs	X		X		X	X	X	▲
Abdominal/Pelvic Exam	X		X		X	X	X	▲

X=protocol-defined procedure; ▲=performed as clinically indicated; Plasma archive will only apply if participant has signed the consent for Storage of Specimens

[figure not shown]

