10.2 Study Endpoints

10.2.1 Primary Endpoint

Consistent with the primary study objective to assess the safety of study drug when administered twice daily for 14 consecutive days on vulvar and cervicovaginal mucosa, the following primary endpoints will be assessed:

- Abnormal genital symptoms judged by the Investigator to be possibly, probably, or definitely related to product use;
- Abnormal pelvic exam findings, (excluding findings observed by colposcopy only), judged by the Investigator to be possibly, probably, or definitely related to product use;
- Grade 3 or higher laboratory values (as defined by the DAIDS Toxicity Tables) for hematology, liver function, creatinine level and coagulation judged by the Investigator to be possibly, probably, or definitely related to product use;
- Adverse experiences judged by the Investigator to be possibly, probably, or definitely related to product use.

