10.10.2 Data Analysis

For analyses comparing VivaGel[®] to the VivaGel[®] placebo, data from approximately 43 women will be included (18 participants in each of the 2 arms plus 7 previously enrolled) whereas for analyses comparing VivaGel[®] to the HEC gel, data from approximately 36 women will be included (18 participants per arm). All references to “control gel” below apply to 1) the VivaGel[®] placebo in analyses comparing VivaGel[®] to the VivaGel[®] placebo and, 2) the HEC gel in analyses comparing VivaGel[®] to the HEC gel.

When the use of descriptive statistics to assess group characteristics or differences is required, the following methods will be used: for categorical variables, the number and percent in each category; for continuous variables, the mean, median, standard deviation, quartiles and range (minimum, maximum). Within-treatment group assessment of the change from the baseline measurement to a follow-up measurement will be analyzed using McNemar’s test (for categorical response variables) or the paired t-test or Wilcoxon signed-ranks test (for continuous variables). When use of formal testing to assess differences between users of the control gel and users of VivaGel[®] is required, the following methods will be used: for binomial response variables, chi-square tests and logistic regression; for continuous variables, t-tests and linear regression or nonparametric methods if data are non-Normal.

To assess the adequacy of the randomization, control gel and VivaGel[®] participants will be compared for baseline characteristics including demographics, pelvic examination, and laboratory measurements using descriptive statistics. Due to the small sample size, formal comparisons will not be done.

Primary Analyses

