The primary aim of the study is to assess the toxicity of VivaGel[®] on vulvar and cervicovaginal mucosa. All visits in which a woman has been exposed to the study product will be included in the primary analysis of safety. Secondary intent to treat analyses may also be performed. To assess safety, the number and the percentages of participants experiencing at least one AE, and the number and percentage experiencing each specific AE will be tabulated by study arm. Each participant will contribute once in each category (i.e. only for highest severity AE for each participant) for the calculation of event rates. The number and percentage of participants experiencing each type of AE (including AEs leading to study discontinuation) will be tabulated by severity and relationship to treatment for each treatment group. AEs that lead to study product discontinuation will be listed in a separate data listing. Overall summaries by treatment group include the number and percentage of participants experiencing: (1) any experience; (2) any moderate, severe, or life-threatening experience. The number and percentage of participants with an AE judged possibly, probably or definitely related to study treatment will be summarized for each treatment group. Grade 3 or higher toxicity for hematology, coagulation function, liver function, or creatinine level is also a primary endpoint. Baseline and Two-Week visit laboratory measures will be summarized and the change in function, defined by the difference between Two-Week and baseline measurements, will be evaluated by treatment group.

Secondary Analyses

One secondary study objective is to assess adherence to a short-term regimen of VivaGel[®]. To assess adherence, the proportion of participants who applied 80% of the expected number of doses of study product over the two weeks of product use will be calculated by treatment arm. All enrolled women will be included in this analysis.

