An additional secondary study objective is to evaluate aspects of product acceptability. To evaluate acceptability, the proportion of participants who at their Two-Week Follow-up Visits report via acceptability questionnaire that they would be extremely likely to use the candidate microbicide during sexual intercourse in the future will be calculated by treatment arm. In addition, positive and negative aspects of using the study drug will be listed in order of frequency. All enrolled women with a Two-Week follow-up visit will be included in these analyses.

The final secondary study objective is to assess the effect of a twice-daily short-term regimen of VivaGel[®] on the vaginal microflora of sexually active HIV-uninfected women. To assess the effect of SPL7013 on vaginal flora, clinically significant changes in vaginal flora will be evaluated by the Nugent score with shift tables from baseline (Enrollment) to follow-up visits. The Nugent score is graded 1 to 10 as follows:

1. Normal, 0 to 3
2. Intermediate, 4 to 6

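### The safety laboratories are measured twice before any gel, but the analysis section names no laboratory baseline visit and gives the Screening 1 value no analytic role

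*Supplement*

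**What the plan says.** Appendix I marks the row "CBC, Liver Function Panel, Creatinine Level, Coag. Panel" as a required procedure at Screening 1, Enrollment, One-Week and Two-Week. Tables 11 and 13 agree. Table 13 places the first dose in the clinic at Enrollment and lists it after blood collection and randomization, so both earlier panels are free of gel.

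Section 10.10.2 describes the laboratory analysis as follows: "the change in function, defined by the difference between Two-Week and baseline measurements, will be evaluated by treatment group". The general rule is also singular: "Within-treatment group assessment of the change from the baseline measurement to a follow-up measurement". Neither sentence names the baseline visit for the laboratories. For between-arm comparisons the section lists "for continuous variables, t-tests and linear regression or nonparametric methods if data are non-Normal" and specifies no baseline adjustment.

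For the Gram stain the visit is named: the Nugent score is shown in "shift tables from baseline (Enrollment) to follow-up visits".

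The primary laboratory endpoint in section 10.2.1 is "Grade 3 or higher laboratory values (as defined by the DAIDS Toxicity Tables) for hematology, liver function, creatinine level and coagulation", judged related to product. It is not a change from baseline. The use of the screening panel that the protocol does describe is eligibility (section 5.3).

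**The concern.** Two gaps sit together. First, two pre-gel panels exist and no visit is named, so the laboratory baseline could be Enrollment, Screening 1 or a mean of the two. That choice should be fixed before the data are seen.

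Second, a single laboratory value carries day-to-day and assay variation, which passes straight into Two-Week minus baseline. With 18 women per arm in the VivaGel versus HEC comparison, a second pre-gel value that is already collected could remove some of that variation. Both values precede randomization, so adjusting for them does not bias the randomized comparison.

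At stake is the precision of the laboratory change comparisons only. These come under the primary analyses in section 10.10.2, but they are not the primary endpoint.

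**Working it through.** **The plan's own figures.** Section 10.4 gives event probabilities only, and they reproduce. At a 5% rate and n = 18, 1 − 0.95^18 = 0.603, against 0.60 in Table 17. The enrollment figure in section 10.9 also follows: 61/0.95 = 64.2, against about 64. Nothing in the plan concerns the precision of a change from baseline, so there is no stated figure to test here.

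**Inputs.** There are 18 women per arm (section 10.4), so N = 36. The correlations are assumptions: r_E (Enrollment with Two-Week), r_S (Screening 1 with Two-Week) and r_SE (Screening 1 with Enrollment). Variances are in units of the single-visit variance, taken as equal across visits.

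**Formulas.**
- Change from Enrollment: 2(1 − r_E)
- Regression on Enrollment: 1 − r_E²
- Regression on both: 1 − (r_E² + r_S² − 2·r_E·r_S·r_SE)/(1 − r_SE²). When all three equal r this is 1 − 2r²/(1 + r).
- Price of estimating k covariate slopes: multiply by (N − 3)/(N − 3 − k), which is 33/32 for one and 33/31 for two. The second covariate therefore costs 32/31 = 1.032, about 3%.

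**Worked case, all correlations 0.7.** Regression on both: 1 − 2(0.49)/1.7 = 0.424. Against Enrollment-only regression: (0.424/0.510) × 32/31 = 0.86. Against the change score: (0.424 × 33/31)/0.600 = 0.75.

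| r_E, r_S, r_SE | Change score | Enrollment only | Both | Both v Enrollment only, net | Both v change score, net |
|---|---|---|---|---|---|
| 0.5, 0.5, 0.5 | 1.000 | 0.750 | 0.667 | 0.92 | 0.71 |
| 0.7, 0.7, 0.7 | 0.600 | 0.510 | 0.424 | 0.86 | 0.75 |
| 0.7, 0.6, 0.6 | 0.600 | 0.510 | 0.459 | 0.93 | 0.82 |
| 0.7, 0.5, 0.5 | 0.600 | 0.510 | 0.480 | 0.97 | 0.85 |
| 0.7, 0.4, 0.4 | 0.600 | 0.510 | 0.493 | 1.00 | 0.87 |
| 0.7, 0.3, 0.3 | 0.600 | 0.510 | 0.501 | 1.01 | 0.89 |
| 0.8, 0.5, 0.5 | 0.400 | 0.360 | 0.347 | 0.99 | 0.92 |

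Simulation at 18 per arm agrees: 0.85 for all correlations 0.7, and 1.02 for 0.7, 0.3, 0.3.

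**Where the gain comes from.** Regression on Enrollment alone already improves on the change score. At r_E = 0.5 the ratio is 0.750 × 33/32 = 0.77; at 0.7 it is (0.510 × 33/32)/0.600 = 0.88; at 0.8 it is (0.360 × 33/32)/0.400 = 0.93. The part due to Screening 1 is the column before the last.

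**The case against.** **No error.** The last value before dosing, taken on the dosing day, is a conventional baseline, and the choice of covariates is often left to a separate analysis plan, which is not shown here. That stands, and it is why this is an optional improvement. It does not settle the unnamed laboratory baseline.

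**Screening 1 is not a true replicate.** It may be up to 36 days old and has no required cycle phase (section 7.6.1), whereas Enrollment falls 1 to 2 days after menses (section 7.6.3). Confirmed Grade 3 or higher values are also screened out. This stands, and the lower rows of the table show the gain disappearing as the Screening 1 correlations weaken. Regression gives a poor second value little weight, so the loss is limited to about 2% over the range tried.

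**Little of it reaches formal inference.** The primary endpoint uses no baseline, and section 10.10.2 has laboratory change evaluated by group without requiring a test. This also stands.

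**The seven Version 2.0 participants.** Their visit schedule is not shown, so two pre-gel panels cannot be confirmed for them. They are 7 of about 43 in the comparison with VivaGel placebo.

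**Stronger readings that the documents do not support.**
- A reader might infer that the plan discards the Screening 1 laboratory value by choice. For the laboratories no baseline visit is named, so what can be shown is an undefined baseline and no described use.
- A reader might expect a 25% cut in variance, as if there were 24 women per arm (18/0.75). That is the ratio 1.5(1 − r)/2(1 − r) for change from the mean of two equally correlated values. It belongs to averaging, not to covariate adjustment. With correlations 0.8, 0.5, 0.5 averaging makes matters worse: 0.45/0.40 = 1.13.
- A reader might extend the point to the Nugent baseline category, since "Gram-Stained Vaginal Smears" are also required at both visits. But that baseline is explicitly Enrollment, the formal between-arm test is on scores at follow-up visits and uses no baseline, and the shift tables are left unchanged here.

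**Conclusion.** The point holds as a minor one, limited to continuous laboratory values. The documents establish two required pre-gel panels, an unnamed laboratory baseline visit and no analytic role for the Screening 1 value.

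The size is conditional on the assumed correlations. Against Enrollment-only regression, variance runs from about 15% lower, when Screening 1 predicts Two-Week about as well as Enrollment does, to about 2% higher when it predicts much less well. Against the simple change score it is about 8% to 29% lower. Correlations outside the table would widen both ranges. Naming the baseline visit is worthwhile whatever the correlations are.

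**What to change.** In section 10.10.2:

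1. Name Enrollment as the baseline for the laboratory change summaries.
2. For between-arm comparisons of continuous laboratory values, use the linear regression already listed, with the Enrollment and Screening 1 values as covariates. Keep the nonparametric option for clearly non-Normal data.
3. Say which screening value is used when a specimen was repeated (Table 12 allows this), and what is done if the value is missing. Check first whether the seven Version 2.0 participants have both panels.
4. Keep the Nugent shift tables on Enrollment, as written.
5. Optionally, show the Screening 1 to Enrollment laboratory change descriptively. Label it as affected by cycle phase and by selection at screening, so that it is not read as a clean gel-free reference.

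The cost is a few sentences, one covariate and, if wanted, one table column. No new sample or visit is needed. The downside is one degree of freedom per model, about 3% of variance at 18 per arm, which is already counted in the net figures.
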